Evaluating Immunogenicity and Safety Effect on Combined Immune Effect of EV71 Inactivated Vaccine and HepB、MPSV-A、MR、JE-L : A Multi-center Randomized Controlled Trial

Registered classification: prevention of biological products

Clinical stage: stage IV

Program number: EV71-2017-03

Version date: 05 01 2018

Bidding unit:

China Biotechnology Limited by Share Ltd

Wuhan biological products research institute limited liability company

Research unit:

Shandong Center for Disease Control and Prevention

Hunan Center for Disease Control and Prevention

Shaanxi Center for Disease Control and Prevention

Shanxi Center for Disease Control and Prevention

Statistical analyses

The quantitative index lists the standard deviation, the median, the maximum and the minimum, and the qualitative index or the grade index list the frequency distribution table. The antibody titers of immunogenicity index should be represented by geometric mean, median, maximum and minimum value and 95% confidence interval. The antibody titer should be analyzed by logarithmic transformation.

A list of the total population, susceptible and non susceptible seroconversion rate and 95% confidence interval, and calculation (test group and control group) rate difference and 95% confidence interval, non-inferiority test; the test group and the control group between the antibody geometric mean (GMT/GMC) compared with the t test after logarithmic transformation P, with less than 0.05 as there were statistically significant differences in the standard.

Arms

Experimental: Combination inoculation group Group I : HepB:3+EV71 Group II : MPSV-A:1+EV71 Group III: MR+EV71 Group IV: JE-L+EV71 Inoculation vaccine made by different techniques(EV71 vaccine 0.5ml per dose, Wuhan Biological Products Co., Ltd., Wuhan, Hubei Province, China; 10 μ g HepB 0.5ml per dose, Wuhan Biological Products Co., Ltd., Wuhan, Hubei Province, China; 30ug MPSV-A 0.5ml per dose, Wuhan Biological Products Co., Ltd., Wuhan, Hubei Province, China; MR 0.5ml per dose, Beijing Biological Products Co., Ltd., Beijing, China; JE-

L 0.5ml per dose, Chengdu Biological Products Co., Ltd., Chengdu, Sichuan Province, China) were given intramuscularly in the deltoid region to participants.

Active Comparator: Separate inoculation control group Group I : HepB:3 Group II : MPSV-A:1 Group III: MR Group IV: JE-L Inoculation vaccine made by different techniques (EV71 vaccine 0.5ml per dose, Wuhan Biological Products Co., Ltd., Wuhan, Hubei Province, China; 10 μ g HepB 0.5ml per dose, Wuhan Biological Products Co., Ltd., Wuhan, Hubei Province, China; 30ug MPSV-A 0.5ml per dose, Wuhan Biological Products Co., Ltd., Wuhan, Hubei Province, China; MR 0.5ml per dose, Beijing Biological Products Co., Ltd., Beijing, China; JE-L 0.5ml per dose, Chengdu Biological Products Co., Ltd., Chengdu, Sichuan Province, China) were given intramuscularly in the deltoid region to participants.

Active Comparator: EV71 inoculation control group Group I : EV71 Group II : EV71 Group III: EV71 Group IV: EV71 Inoculation vaccine made by different techniques (EV71 vaccine 0.5ml per dose, Wuhan Biological Products Co., Ltd., Wuhan, Hubei Province, China; 10 μ g HepB 0.5ml per dose, Wuhan Biological Products Co., Ltd., Wuhan, Hubei Province, China; 30ug MPSV-A 0.5ml per dose, Wuhan Biological Products Co., Ltd., Wuhan, Hubei Province, China; MR 0.5ml per dose, Beijing Biological Products Co., Ltd., Beijing, China; JE-L 0.5ml per dose, Chengdu Biological Products Co., Ltd., Chengdu, Sichuan Province, China) were given intramuscularly in the deltoid region to participants.

Assigned Interventions

Biological/Vaccine: Inoculation vaccine EV71 vaccine 0.5ml per dose, Wuhan

Biological Products Co., Ltd., Wuhan, Hubei Province, China 10µg HepB 0.5ml per dose, Wuhan Biological Products Co., Ltd., Wuhan, Hubei Province, China 30ug MPSV-A 0.5ml per dose, Wuhan Biological Products Co., Ltd., Wuhan, Hubei Province, China MR 0.5ml per dose, Beijing Biological Products Co., Ltd., Beijing, China JE-L 0.5ml per dose, Chengdu Biological Products Co., Ltd., Chengdu, Sichuan Province, China

Outcome Measures

Primary Outcome Measure:

1. Statistical analysis of immunogenicity 1. Serum antibody positive rate, antibody 4 times growth rate, antibody positive rate (4 times increase) rate and confidence interval, and non-inferiority test of antibody positive rate 2. Antibody titer / concentration distribution before and after immunization.

2. Secondary Outcome Measure:

2. Population characteristics of the subjects 1. Demographic equilibrium and basic statistical indicators 2. the number of entering, completing, falling off, deviating from the scheme and the reasons
3. Statistical analysis of Clinical safety
 1. the occurrence of undesirable events, non-collection events, falling off and serious adverse events 2. the occurrence of adverse events at different severity levels 3. the occurrence of symptoms of adverse reactions at different severity levels 4. Special attention should be given to the cases of termination or withdrawal due to adverse events and serious or serious adverse events, and

lists detailed account of falling off, termination / exit, deviation / violation,
adverse events and serious adverse events.

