Evaluating Immunogenicity and Safety Effect on Combined Immune Effect of EV71 Inactivated Vaccine and HepB、MPSV-A、MR、JE-L : A Multi-center Randomized Controlled Trial

Registered classification: prevention of biological products

Clinical stage: stage IV

Program number: EV71-2017-03

Version date: 05 01 2018

Bidding unit:

China Biotechnology Limited by Share Ltd

Wuhan biological products research institute limited liability company

Research unit:

Shandong Center for Disease Control and Prevention

Hunan Center for Disease Control and Prevention

Shaanxi Center for Disease Control and Prevention

Shanxi Center for Disease Control and Prevention

Background

To prevent and control the epidemic of HFMD and related diseases caused by EV71 infection, the development of EV71 vaccine has been developed in many countries or regions. According to the requirements of drug registration approval, we need to evaluate immunogenicity and safety effect on combined immune effect of EV71 inactivated vaccine and other vaccines (HepB、MPSV-A、MR、JE-L).

Method

Four experimental groups (HepB:3+EV71, MPSV-A:1+EV71, MR +EV71, JE-L+EV71) were included in this clinical trial. In addition to the meningococcal vaccine research group, the other three groups were followed up for the 4 times. The initial blood samples were collected, and the first dose vaccine was inoculated at the same time. EV71 second doses of vaccine were inoculated at 30 day, the blood was collected after 30 days of immunization with second doses. 6 months of safety follow-up was carried out in the whole clinical trial after vaccination. The meningococcal vaccine research group increased 1 follow-up after the second dose of MPSV-A vaccine. The index of immunogenicity and safety effect in four experimental groups need to be evaluated.

Study design and participants

The study was conducted in four provinces (Shandong, Shanxi, Shaanxi and Hunan) of China, which contains Haiyang city, Rushan city, Shimen County, Chen Cang District, Qishan County, Taigu County and Qi County. 6/8 months children were

recruited in this study, individuals were randomly assigned to experimental group and control group. Demographic information (age, sex, height and weight) was made and blood samples were collected for each individual in the same way.

Inclusion Criteria

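### Free improvement: stratify the non-inferiority rate difference by baseline serostatus for EV71, and for MR and JE-L where the response rule covers both baseline groups

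*SAP*

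**What the plan says.** The SAP, Statistical analyses, specifies for the rates a "calculation (test group and control group) rate difference and 95% confidence interval, non-inferiority test". It names no interval method, weighting, stratification or covariate. The sentence opens with "A list of the total population, susceptible and non susceptible seroconversion rate and 95% confidence interval", so baseline serostatus is used, but no estimate combining the two groups is described. Under Outcome Measures the primary outcome includes a "non-inferiority test of antibody positive rate".

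The Protocol plans the data needed. Its Method section says "The initial blood samples were collected, and the first dose vaccine was inoculated at the same time", and Study design and participants adds that "blood samples were collected for each individual in the same way". Randomisation is by individual, with no stratification factor stated.

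The Protocol's Immunogenicity end point section defines response antigen by antigen:
- **EV71:** a threshold rule when the baseline titre is below 1:8, and a fourfold rise when it is above.
- **JE-L:** a rule for baseline below 1:5, or a fourfold rise.
- **MR:** thresholds for measles and rubella, with a fourfold rise that appears to apply to infants positive at baseline.
- **HepB:** seroconversion is defined only for infants with anti-HBs below 10 mIU/ml before the dose.
- **MPSV-A:** a fourfold rise, with no susceptibility cut-off.

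**The concern.** For EV71, a susceptible infant responds by crossing a threshold, while a non-susceptible infant must show a fourfold rise from a titre that is already measurable. Baseline serostatus may therefore predict response strongly. If it does, a difference that ignores it carries between-group variation that a stratified estimate removes.

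The lower confidence limit decides a non-inferiority test, so unneeded width costs power. EV71 has its own control group in all four Tests, so the point arises four times. With crude, subgroup and adjusted results all possible and none named as decisive, the choice is also left open until the data are seen.

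**Working it through.** **Nothing to reproduce.** The documents state no sample size, margin, power or expected rate. Every rate, share and sample size below is an assumption.

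**Formula.** Take equal arms of n infants, no true difference, a fraction q non-susceptible with response b, and a fraction 1-q susceptible with response a.
- Overall rate: P = (1-q)a + qb
- Variance of the crude difference: 2P(1-P)/n
- Variance of the stratified difference: 2W/n, where W = (1-q)a(1-a) + qb(1-b)
- Ratio of interval widths: √(W / [P(1-P)]), which does not depend on n

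**Serostatus.**

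| q | a | b | W | P(1-P) | W / P(1-P) | Interval narrower by |
|---|---|---|---|---|---|---|
| 10% | 98% | 90% | 0.02664 | 0.02722 | 0.979 | 1.1% |
| 20% | 98% | 80% | 0.04768 | 0.05286 | 0.902 | 5.0% |
| 20% | 98% | 60% | 0.06368 | 0.08678 | 0.734 | 14.3% |
| 40% | 95% | 40% | 0.12450 | 0.19710 | 0.632 | 20.5% |
| any | a = b | a = b | P(1-P) | P(1-P) | 1 | 0% |

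The first four rows are selected cases, not bounds. Other pairings of the same inputs go a little further each way:
- q = 10%, 95% vs 90%: √(0.05175/0.05198) = 0.998, or 0.2% narrower.
- q = 20%, 98% vs 40%: √(0.06368/0.11750) = 0.736, or 26% narrower.

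**In points.** For q = 20%, 98% vs 60% and n = 150 per arm:
- Crude: 1.96 × √(2 × 0.08678/150) = ±6.67 points
- Stratified: 1.96 × √(2 × 0.06368/150) = ±5.71 points

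**Simulation check.** This used 20,000 trials per scenario and compared the crude Wald interval with the Mantel-Haenszel difference.
- In the same case the mean half-widths were ±6.63 and ±5.67 points, in line with the formula.
- Power against an assumed 10-point margin rose from 83% to 93%. With 10% seropositive and 98% vs 90%, it was 99.7% vs 99.8%, so there was nothing to gain.
- Coverage of the crude interval was 94.7% to 95.6% in every scenario.

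**Site.** With seven equal sites evenly spaced from 90% to 98%:
- P(1-P) = 0.94 × 0.06 = 0.0564
- Between-site variance = (0.08/6)² × (7² - 1)/12 = 0.00071
- Variance falls by 0.00071/0.0564 = 1.3%, and width by 0.6%

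For 80% to 98%, width falls by 1.9%. In simulation at n = 150 per arm, the 90-98% case showed no gain (±5.33 crude, ±5.35 stratified).

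**The case against.** The strongest reply is that the SAP is silent rather than wrong. It states no method, and the run-on sentence could mean that rates, differences and tests are all given for the total, susceptible and non-susceptible groups. That stands, and it is why the request is to specify an estimate, not to correct one.

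The gain also cannot be shown from the documents. The inclusion criteria of all four Tests exclude a history of EV71 infection, which may make non-susceptible infants few. If the tested positive rate means simply being above the threshold after vaccination, the contrasts assumed above do not apply. Both points stand; they set the range and do not remove the case for an almost costless step.

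A reader might infer more, in three ways that the documents do not support:
- **That chance imbalance in serostatus makes the crude comparison unsound.** With q = 20%, 98% vs 60% and n = 150 per arm, a one-SD imbalance is √(2 × 0.2 × 0.8/150) = 4.6 points, which moves the difference by 4.6 × 0.38 = 1.8 points. Under individual randomisation the crude interval already allows for this, as its coverage shows.
- **That site should also be a stratum.** The gain is about 0-2% of width. The Protocol lists seven places for the whole study ("which contains Haiyang city, Rushan city, Shimen County, Chen Cang District, Qishan County, Taigu County and Qi County") but does not say how Tests I-IV are spread over them, so one comparison may involve only one or two.
- **That every antigen needs the change.** HepB seroconversion has only one baseline group, and MPSV-A has no stated cut-off by which to form two.

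**Conclusion.** The point holds as a free or cheap improvement in efficiency and pre-specification, not as an error. The crude 95% interval is valid. Stratifying by baseline serostatus would narrow it by 0% if serostatus is not prognostic and by about 1% to 20% in the worked cases, somewhat more at the most favourable pairing of the same inputs. These figures assume equal arms, no true difference, and response rates and seropositive shares that the documents do not give.

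The argument is firmest for EV71, whose rule changes with baseline titre and which is compared in all four Tests. It extends to MR and JE-L only so far as their rules cover both baseline groups; the MR wording is unclear on this. The absence of a stated margin and sample size matters more to the trial's conclusion, but supplying them would still leave the estimator unnamed.

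**What to change.** In the SAP, Statistical analyses:
1. For the EV71 comparison in each of the four Tests, make the primary estimate a Mantel-Haenszel or stratified Miettinen-Nurminen risk difference with 95% interval, stratified by baseline serostatus (susceptible or non-susceptible). Base the non-inferiority test on that interval.
2. Do the same for MR and JE-L where the response rule covers both baseline-negative and baseline-positive infants, using serostatus for the antigen concerned.
3. State the baseline cut-off that defines susceptible for each of these antigens, consistent with the Protocol's Immunogenicity end point section.
4. Keep the crude difference as supportive, and keep the separate listings by serostatus.
5. Leave HepB seroconversion and MPSV-A unstratified, and do not add site as a stratum.

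The cost is SAP wording and one standard procedure on serum already planned for collection. The downside is small: if very few infants are seropositive, the strata collapse to the crude difference, and the SAP should say so in advance.

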Inclusion criteria for group I (HepB:3+EV71) were as follows: (1)aged ≥ 6 months; (2)sign the informed consent form; (3)the legal guardian participate in all the planned follow-up and be able to comply with all research procedures; (4)the subjects have completed the basic immunization of 2 needle recombinant hepatitis B vaccine, there is no inoculation history of EV71 vaccine, and there is no history of EV71 infection ; (5)the last vaccination intervals ≥ 14 days ; (6)temperature $\leq 37C^{\circ}$

Inclusion criteria for group II (MPSV-A:1+EV71) were as follows: (1)aged ≥ 6 months; (2)sign the informed consent form; (3)the legal guardian participate in all the planned follow-up and be able to comply with all research procedures; (4)there is no inoculation history of EV71 vaccine, and there is no history of EV71 infection; (5)the last vaccination intervals ≥ 14 days ; (6)temperature $\leq 37C^{\circ}$

Inclusion criteria for group III (MR+EV71) were as follows: (1)aged ≥ 8 months; (2)sign the informed consent form; (3)the legal guardian participate in all the planned follow-up and be able to comply with all research procedures; (4)there is no inoculation history of EV71 vaccine, and there is no history of EV71 infection; (5)the last vaccination intervals ≥ 14 days and the last attenuated live vaccine intervals ≥ 28 days ; (6)temperature $\leq 37C^{\circ}$

Inclusion criteria for group IV (JE-L+EV71) were as follows: (1)aged ≥ 8 months; (2)sign

the informed consent form; (3)the legal guardian participate in all the planned follow-up and be able to comply with all research procedures; (4)there is no inoculation history of EV71 vaccine, and there is no history of EV71 infection; (5)the last vaccination intervals ≥ 14 days and the last attenuated live vaccine intervals ≥ 28 days ; (6)temperature $\leq 37C^{\circ}$

Exclusion Criteria

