Detection of serum antibody EV71 vaccine by culture neutralization test, the definition of positive for neutralizing antibody titers of $<1:8$ before inoculation, inoculation after neutralizing antibody titers than $1:8$; or before inoculation neutralizing antibody titer is above $1:8$, the titer of neutralizing antibody after vaccination appeared more than 4 times the growth. Hepatitis B vaccine seroconversion was defined as Anti-HBs $<10\text{mIU/ml}$ before inoculation, Anti-HBs after inoculation was more than 10mIU/ml . Leprosy vaccine using measles rubella immunoglobulin ELISA detection test, measles $>200\text{U/ml}$ positive for rubella $>20\text{U/ml}$ positive or positive before inoculation; after inoculation, antibody positive growth is more than 4 times. Japanese encephalitis vaccine serum samples by using PRNT test before immunization antibody titer after inoculation was less than $1:5$, at $1:10$, or after vaccination antibody titer than before inoculation is no less than 4 times of growth is positive. Meningococcal vaccine samples A meningococcal bactericidal antibody level in serum by micro bactericidal antibody test, the antibody titer after inoculation than before inoculation is no less than 4 times of growth is positive.

Safety assessment

Safety assessment Participants were provided with diary cards to record the

occurrence and severity of solicited local reactions at the injection site (pain, induration, erythema, edema, pruritus) during 7 days after vaccination, solicited systemic reactions (fever, headache, fatigued, cough, myalgia, asthenia, vertigo, diarrhea), and any unsolicited adverse during 29 days after vaccination.

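### The GMT/GMC comparison is an unadjusted t test although a pre-dose titre of the same antigen is available; adjusting for it would sharpen the contrast at almost no cost

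*SAP*

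**What the plan says.** The SAP, Statistical analyses, gives one method for comparing antibody levels between arms: "the antibody geometric mean (GMT/GMC) compared with the t test after logarithmic transformation", with significance judged at P "with less than 0.05 as there were statistically significant differences in the standard". It names no baseline covariate, change-from-baseline analysis or centre term. It also does not name the time point. That the test is on post-dose values is an inference, but a comparison of vaccine effect makes sense only there.

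The pre-dose value is collected and used elsewhere:

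- Protocol, Method: "The initial blood samples were collected, and the first dose vaccine was inoculated at the same time". The later sample is described as "the blood was collected after 30 days of immunization with second doses", with test-specific visits listed under Vaccine inoculation and follow-up.
- Protocol, Immunogenicity end point: the response definitions refer to the level before inoculation. For EV71 one limb reads "before inoculation neutralizing antibody titer is above $1:8$, the titer of neutralizing antibody after vaccination appeared more than 4 times the growth".
- SAP, Outcome Measures, primary: "Antibody titer / concentration distribution before and after immunization".
- SAP, Statistical analyses: "A list of the total population, susceptible and non susceptible seroconversion rate and 95% confidence interval". This split by baseline status is written for rates and is not carried into the GMT/GMC comparison.

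**The concern.** The plan treats pre-dose status as relevant to the seroconversion rates and ignores it for the titres. Where the pre-dose level predicts the post-dose level, an unadjusted test leaves that variation in the error term. The interval for the arm contrast is then wider than the data allow, and a real drop in antibody level under co-administration is harder to detect. A chance difference between arms in pre-dose titre also passes into the contrast in proportion to the pre/post slope. Tabulating demographic balance or pre-dose titres would show such a difference but would not correct for it.

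The documents expect pre-dose levels to vary in at least one test. Test I requires that "the subjects have completed the basic immunization of 2 needle recombinant hepatitis B vaccine", so anti-HBs before the third dose should differ between infants. The EV71 and measles/rubella definitions also allow for infants who are positive before inoculation.

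**Working it through.** **Inputs.** From the documents: a t test on log values, a 0.05 level (two-sided assumed, since sidedness is not stated), individual randomization, and a pre-dose sample. The documents give no sample size, SD, target GMT ratio or pre/post correlation, so there is no stated figure to reproduce. The within-arm correlation ρ of pre- and post-dose log titre is therefore an assumption, taken from 0 to 0.7.

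**Step 1, precision.** With equal arms, the variance of the log-GMT difference is 2σ²/n for the t test and about 2σ²(1 − ρ²)/n after adjustment. The variance ratio is 1 − ρ², the interval-width ratio is √(1 − ρ²), and the equivalent gain in sample size is 1/(1 − ρ²) − 1. If the t test had 80% power, adjusted power is Φ[(1.96 + 0.842)/√(1 − ρ²) − 1.96].

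| Assumed ρ | Variance cut | Interval-width ratio | Equivalent extra infants | Power, from 80% |
|---|---|---|---|---|
| 0 | 0% | 1.000 | 0% | 80.0% |
| 0.1 | 1% | 0.995 | 1% | 80.4% |
| 0.3 | 9% | 0.954 | 10% | 83.6% |
| 0.5 | 25% | 0.866 | 33% | 89.9% |
| 0.7 | 49% | 0.714 | 96% | 97.5% |

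A simulation with an assumed 100 infants per arm and 10,000 runs per ρ gave variance ratios of 1.01, 0.91, 0.75 and 0.51 for ρ of 0, 0.3, 0.5 and 0.7.

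**Step 2, an illustration in titre units.** Assume SD 0.6 log10, 100 infants per arm and a true GMT ratio of 0.67. Then SE = 0.6 × √(2/100) = 0.085 and −log10(0.67) = 0.174. Power is Φ[0.174/(0.085 × √(1 − ρ²)) − 1.96], which is 54% at ρ = 0 and 57%, 66% and 82% at ρ of 0.3, 0.5 and 0.7 (unrounded SE used).

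**Step 3, chance imbalance.** In the same simulation the t test's overall type I error was 4.9% to 5.4%. Given a pre-dose imbalance of c standard errors and no true effect, the test statistic is distributed as N(ρc, 1 − ρ²). Its false-positive rate is P(|Z| > 1.96):

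| Assumed ρ | c = 1 | c = 2 |
|---|---|---|
| 0.1 | 5.0% | 5.3% |
| 0.3 | 5.0% | 8.1% |
| 0.5 | 4.8% | 13.4% |
| 0.7 | 3.9% | 21.7% |

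**Step 4, an illustration of the shift.** Assume a pre-dose SD of 0.6 log10 as well, and a positive slope of 0.5. A pre-dose gap of 0.15 log10 is 0.15/0.085 = 1.77 SE, and a gap at least that large in either direction has about an 8% chance per contrast. It moves the contrast by 0.5 × 0.15 = 0.075 log10, so a true ratio of 1.00 would be estimated as 10^(−0.075) = 0.84.

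**The case against.** The strongest reply is that nothing here is wrong. A t test on log titre is a valid comparison under individual randomization, and no passage contradicts it. That stands: a reader might infer that the GMT/GMC contrasts are biased or that their error rate is inflated, but overall type I error is near 5%. The inflation in Step 3 is conditional on a large imbalance, and the rate is at or slightly below 5% at one standard error.

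A reader might also infer that the trial's non-inferiority conclusion is weakened. The documents do not support this. The SAP attaches the non-inferiority test to the antibody positive rate. Titre distribution is listed under the primary outcome, but no decision rule rests on it.

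The size is assumed throughout, which also stands. Near ρ = 0 there is nothing to gain, and even at 0.3 the illustrated power moves only from 54% to 57%. Prior vaccination with the antigen is documented only for HepB in Test I. All four tests exclude a history of EV71 vaccination or infection, and MPSV-A, MR and JE-L start at the first dose. A correlation of 0.5 to 0.7 for every antigen would be unsupported.

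The imbalance example in Step 4 is modest. A shift of 0.075 log10 is 0.88 SE of the contrast (two-sided P about 0.38), so it would not by itself produce a significant result. A negative slope would reverse its direction, and a smaller pre-dose SD would make such a gap rarer. Nor should the point rest on the arms being open-label: neither document describes masking, and masking has no bearing on chance differences in a sample taken before dosing takes effect.

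What the reply does not answer is why a value already collected, used for the response definitions and reported should be left out of the one test of antibody level.

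**Conclusion.** The point holds as an improvement in efficiency, not as the correction of an error. The planned t test is valid but is less precise than the data allow whenever pre- and post-dose log titres are correlated, and it offers no protection from a chance pre-dose imbalance. Across the assumed range the variance reduction runs from nothing to about half. The documents do not show where in that range each antigen lies. On the eligibility criteria, anti-HBs in Test I is the likeliest to benefit materially. For antigens where nearly all infants are below the assay limit before dosing, expect little. The conclusion rests on three readings: that the t test is applied to post-dose values, that it carries no covariate, and that the pre-dose sample is assayed for the antigen being compared.

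**What to change.** In the SAP, Statistical analyses, make the main GMT/GMC analysis a linear model of post-dose log titre (or concentration) on arm, adjusted for pre-dose log titre of the same antigen. Fit it per antigen, comparing the combined arm with the control that received that antigen. Specifically:

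- State the post-dose time point for each test.
- State the value assigned to results below the assay limit, and add an indicator for below-limit pre-dose values where these are not nearly universal. Where they are, the covariate carries almost no information.
- Study site may be added as a further covariate. This is optional, since no figure in the documents shows what it would gain.
- Report the back-transformed adjusted GMT/GMC ratio with its 95% confidence interval.
- Keep the t test as a sensitivity analysis.
- Fix the model before any between-arm results are seen.

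The cost is a few sentences in the SAP, with no new visit, blood draw or assay. The downside is that infants without a pre-dose sample drop out of the adjusted model. Report their number by arm. The t test on all infants with a post-dose result then helps show whether their omission matters.
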